1. INTRODUCTION

[Note: In this document, any text taken directly from the protocol is italicized.]

The purpose of this document is to provide further details about the statistical analysis methods specified in the study protocol B1801023. *Protocol B1801023 is an 8-year extension study designed to further characterize the long-term safety profile, malignancy and other serious adverse events, and clinical benefit for those pediatric subjects who received at least one dose of etanercept and completed 96 weeks of investigational product and/or follow-up in study 0881A1-3338-WW (B1801014). The previous study was designed to assess the clinical benefit and the long-term safety of etanercept for 2 years (96 weeks) in pediatric subjects with extended oligoarticular juvenile idiopathic arthritis, enthesitis-related arthritis (ERA), or psoriatic arthritis (PsA).*

Based on the lack of information regarding when treatment with etanercept should be discontinued and the success of re-treatment if relapse occurs, this protocol is being amended to also explore clinical benefit and physical function after withdrawal of etanercept and after disease relapse occurs.

A brief description of the study objectives and the study design are given in [Section 2](#). Subsequent sections include the definitions of baseline, efficacy and safety endpoints, and analysis populations followed by details about statistical methods. Any major deviations from the methods specified in this document and the protocol must be discussed in the clinical study report.

In order to evaluate overall safety in the most meaningful way, data from the 8 year extension study should not be analyzed independent of the data collected during the preceding 2 year parent study. Therefore, most of the safety analyses will be based on the combined data from the parent study and the subsequent extension. The resulting data summaries and analyses will cover the entire period of up to 10 years. In some cases, in order to fully address the entire etanercept experience, data from subjects who were in the parent study but were never enrolled in the extension study will be included in determining overall rates. Details will be provided in the following sections.

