2.2. Study Design

2.2.1. Basic Features of the Study Design

This is an open-label, single treatment, multi-center, 8-year extension study in pediatric subjects who have been diagnosed with one of 3 subtypes of JIA (eoJIA, ERA, or PsA), have received at least one dose of etanercept and completed approximately 96 weeks of participation in study 0881A1-3338-WW (B1801014). These subjects will be asked to participate in study B1801023. It is anticipated that approximately 100 subjects will be enrolled in study B1801023. This 96-month study contains 3 periods: an active treatment period, a withdrawal/re-treatment period, and an observational period.

Active treatment period

Subjects who completed approximately 96 weeks of active treatment with investigational product (etanercept) in study 0881A1-3338-WW (B1801014) and are eligible to continue investigational product in study B1801023 will enter directly into the active treatment period. These subjects may continue to receive investigational product for up to 8 additional years (96 months).

Withdrawal/Re-treatment period

Withdrawal: Subjects who have either completed approximately 96 weeks of treatment in study 0881A-3338 or were enrolled in the active treatment period of study B1801023 and who have either met the Wallace definition for clinically inactive disease for at least 6 months on investigational product (etanercept) or who, in the investigators judgment, have had a good clinical response and would benefit from withdrawal from investigational product and are otherwise eligible can enter the withdrawal/re-treatment period. However, the withdrawal/re-treatment period is optional and it is ultimately up to the investigator and subject to determine when the subject should be withdrawn from treatment.

Re-treatment: Subjects requiring re-treatment per the investigator's clinical judgment and who are otherwise eligible will be offered the option to re-start treatment with investigational product.

Subjects may not enter the withdrawal/re-treatment period more than once during the study.

Observational period

All subjects will be followed for a total of 8 years from the time of initial entry into the study as follows:

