Subjects who discontinue investigational product prior to completing 96 weeks of active treatment in study 0881A1-3338-WW (B1801014) for any reason or who are not eligible to continue investigational product in study B1801023 will not be permitted to re-start investigational product in study B1801023 and will be asked to enter the observational period. Subjects who participate in the active treatment period of study B1801023 and subsequently discontinue use of investigational product at any time before completion of the study and do not participate in the withdrawal/re-treatment period for any reason (i.e., ineligible or subject declined participation) will be asked to participate in the observational period. Subjects who participate in the withdrawal period and are ineligible for re-treatment with investigational product for any reason will be asked to participate in the observational period. Subjects who participate in the re-treatment period and subsequently discontinue investigational product prior to the completion of the study will be asked to participate in the observational period.

Once a subject enters into the observational period, he or she cannot resume investigational product for the remaining time in the study. Subjects participating in the observational period of study B1801023 may receive standard of care including any anti-TNF agents (eg, commercial etanercept) and/or other biologic agents for treatment of their disease at the discretion of the investigator.

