3.2. Withdrawal Analysis Set

The withdrawal analysis set (WAS) will include those subjects who entered the withdrawal period. Only data collected in the withdrawal period will be included.

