4.2.2. Secondary Endpoints

The secondary endpoints include

- *the occurrence of serious adverse events (SAE, infectious and non-infectious events will be summarized separately),*
- *the occurrence of medically important infections (ie, an infection requiring hospitalization and /or parenteral [intravenous (IV), intra-muscular (IM)] anti-infective agents).*
- Hospitalization: For any hospitalizations, the admission date, discharge date and reason for hospitalization will be collected during the study.
- Death: For any deaths, date of death and cause of death will be collected during the study.

- Nonstudy medication: nonstudy medications are coded using the WHO Drug Dictionary (2006 Q3). The Prior, Concomitant, After (PCA) flag for nonstudy medications will be derived for both parent study and extension study (only for active treatment period):
 - Prior nonstudy medications are defined as any nonstudy medications taken before the first dose of investigational product taken at the start of the study,
 - Concomitant nonstudy medications are defined as any nonstudy medications taken during the treatment period (from the first dose to the last dose of the investigational product).
 - After nonstudy medications refer to any nonstudy medications taken after the last dose of the investigational product.(not applicable for observational period)
- Exposure: the total number of doses taken and exposure time.

The above endpoints will be collected for all subjects. The following endpoints will be collected only for subjects in the active treatment period, or withdrawal/re-treatment period in the extension study:

Non-serious adverse Events (Adverse events that occur up to 30 days after the last dose of investigational product will be counted as having occurred during the treatment period) This is applied for active and retreatment periods. If an AE started in active or retreatment period and continued into withdrawal or observational period, it will be only counted in active or retreatment period, it will not be counted in withdrawal or observational period again. If an event started in withdrawal or observational period, and after 30 days of the last dose of investigational product of active period or re-treatment period, this event will not be counted.

Occurrence of withdrawals from investigational product due to adverse events;

Laboratory evaluations (ie, hematology, blood chemistry, and CRP)

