5.9. Efficacy Endpoints

Descriptive summary statistics will be provided for efficacy endpoints. For continuous endpoints, the summary statistics at each visit will include the number of observations, mean, standard deviation, median, minimum, maximum and 95% confidence interval for the mean. These statistics will be provided for the observed value and change from baseline. The mean percent change from baseline will be provided also. For categorical endpoints, the summary statistics will contain the frequency, percentage, and 95% confidence interval (CI) for the percentage.

These summaries will be performed for:

- FAS, active period data (both parent and extension studies. Baseline of parent study will be used for calculation of change from baseline). The reports will show the baseline (no baseline for ACRPedi responses), weeks 12, 24, 48, and 96 from the parent study and all visits from the extension study where data is collected.
- WAS. The reports will show all visits where data is collected.

- RTAS. Re-treatment period baseline will be used for calculation of change from baseline. The reports will show all visits where data is collected.

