5.16. Data Derivation and Missing Data Handling

The following rules will be used to derive the endpoints and handle the missing components. If an endpoint is missing after derivation, the missing value will not be imputed.

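### By-visit efficacy covers only subjects still in the active period, and good and poor responders can both leave it, so late-visit response rates may over- or understate response in the treated cohort

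*SAP*

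**What the plan says.** **Efficacy summary.** SAP 5.9 summarizes efficacy by visit on "FAS, active period data (both parent and extension studies. Baseline of parent study will be used for calculation of change from baseline"). For response endpoints, "the summary statistics will contain the frequency, percentage, and 95% confidence interval (CI) for the percentage". The readable text does not state the denominator of that percentage.

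**Missing data.** SAP 5.16: "If an endpoint is missing after derivation, the missing value will not be imputed".

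**Horizon.** SAP 1 says, in its discussion of safety data, "The resulting data summaries and analyses will cover the entire period of up to 10 years". SAP 5.9 joins the parent and extension studies in the same way for efficacy.

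**Exits from the active period.** SAP 2.2.1 and Protocol 3 give two routes:
- Subjects with at least 6 months of clinically inactive disease on drug, or with a good response in the investigator's judgment, may enter the withdrawal/re-treatment period. This is optional.
- Those who "subsequently discontinue use of investigational product at any time before completion of the study" and do not take that route are asked to enter observation.

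**Efficacy after exit.** SAP 4.2.2 introduces its list of non-serious adverse event, laboratory, growth and efficacy endpoints with: "The following endpoints will be collected only for subjects in the active treatment period, or withdrawal/re-treatment period in the extension study". The observational visits in Protocol 6.1.6 collect safety and medication data only. For the withdrawal analysis set (WAS), SAP 3.2 says "Only data collected in the withdrawal period will be included". SAP 3.3 applies the same rule to the re-treatment set (RTAS).

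**Disposition.** SAP 5.3 counts subjects who began in the active period and later moved to withdrawal/re-treatment or observation, with reasons for switching.

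**The concern.** The long-term effect of etanercept on clinical benefit and physical function is a secondary objective (Protocol 2.1, SAP 2.1), and the active-period tables are the main evidence for it. The group behind each late percentage is selected on the outcome being summarized. Entry to withdrawal rests on inactive disease or good response. At the other end, Protocol 5.3.1 prohibits other TNF inhibitors and immunosuppressive biologics in the active period, while Protocol 3 allows them in observation, so a subject who needs one cannot stay in the active-period percentage.

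The two exits push the rate in opposite directions. That does not make it unbiased; a reader cannot tell which exit dominates. A high rate at Month 96 could reflect sustained benefit or the loss of failures, and a falling rate could reflect loss of effect or the departure of the best responders.

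Efficacy also differs here from safety and exposure, which pool active and re-treatment periods as on-drug time (SAP 5.5, 5.6, 5.11). A re-treated subject is back on drug but does not return to the active-period efficacy tables.

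**Working it through.** **Inputs from the documents.** Expected enrolment is about 100 across all periods (SAP 2.2.3). No response rate, exit rate or number starting in the active period is given, so there is no plan figure to reproduce. All numbers below are assumptions chosen to show how the estimate behaves.

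**1. Fixed cohort, varying exits.** Assume 100 subjects start, of whom 70 would be responders at a late visit. By then F non-responders and G responders have left.

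Observed-case rate = (70 − G) / (100 − F − G)

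| F | G | Calculation | Observed-case rate |
|---|---|---|---|
| 0 | 0 | 70/100 | 70.0% |
| 20 | 0 | 70/80 | 87.5% |
| 0 | 30 | 40/70 | 57.1% |
| 20 | 30 | 40/50 | 80.0% |
| 25 | 20 | 50/55 | 90.9% |
| 10 | 50 | 20/40 | 50.0% |

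The rate equals 70% only when 0.3G = 0.7F, that is, when leavers have the same responder mix as the cohort. For example, F = 12 and G = 28 gives 42/60 = 70%. The two biases cancel only in that case.

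**2. Same observed rate, different cohorts.** Fix the observed-case rate at 80% of n = 100 − F − G remaining subjects, giving x responders.

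| F | G | x/n | All leavers non-responders, x/100 | Only failures non-responders, (x + G)/100 | All leavers responders, (x + F + G)/100 |
|---|---|---|---|---|---|
| 20 | 20 | 48/60 | 48% | 68% | 88% |
| 50 | 20 | 24/30 | 24% | 44% | 94% |
| 20 | 50 | 24/30 | 24% | 74% | 94% |

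Clopper-Pearson 95% intervals for the observed rates are 67.7–89.2% (48/60) and 61.4–92.3% (24/30). They cover sampling error among those who remain and say nothing about the leavers.

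**3. How many might leave.** Under a constant annual exit rate q, 100 × (1 − q)^8 remain after 8 years: 66, 43, 27 and 17 for q = 5%, 10%, 15% and 20%.

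**4. A further loss with age.** SAP 4.2.2 treats the CHAQ component of ACR Pedi as missing from age 18. Under the SAP 5.16.4 table, with one component missing, the outcome is missing if one component worsens and at least two improve, or if none worsens and exactly two improve. This can shrink the late-visit denominator further as subjects grow up.

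**The case against.** Much of the information needed already exists. SAP 5.9 also reports efficacy for WAS and RTAS at every visit with data, so subjects who enter withdrawal keep full efficacy follow-up. The early withdrawal visit (Protocol 6.1.4) records both global assessments, joints, stiffness, CRP and CHAQ/HAQ, so status at exit is captured. SAP 5.3 gives exit counts and reasons, and SAP 5.11 may add numbers on drug by year. The study is an open-label, single-treatment safety extension with malignancy as primary endpoint. Efficacy is secondary and descriptive, and the SAP labels the summary as active-period data without claiming that it represents the whole cohort.

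All of this stands, and it rules out three stronger readings:
- **That leavers disappear from efficacy reporting.** Only those in observation do. Subjects in withdrawal or re-treatment are reported, but in separate tables.
- **That late rates will be inflated.** The documents give no exit rates, and step 1 shows errors in both directions.
- **That the plan contains no fixed-denominator or imputed analysis anywhere.** The FAS definition was not available for this review, Protocol 9.2.2 breaks off in the available text, and the protocol's abbreviation list includes LOCF. Observed case is an inference from SAP 5.9 and 5.16. If the full FAS were the denominator instead, every leaver would count as a non-responder, including those who left in good response.

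What remains is that no readable analysis links exits to response on one denominator, and that the by-visit denominator is unstated.

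**Conclusion.** The point holds in this form: on the readable text, late-visit active-period response rates describe subjects still in that period and can over- or understate response in the treated cohort. With an assumed true rate of 70%, the illustrations run from 50.0% to 90.9%. Size and net direction in this trial are unknown.

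The conclusion rests on three things: observed case is the correct reading of SAP 5.9 with 5.16; exits are related to response, which the withdrawal criteria make explicit and the prohibited-medication rules make likely for failures; and step 1 simplifies by giving each leaver a fixed responder status. No test, sample size or primary analysis is affected. It is a cheap improvement that changes what can be concluded about long-term benefit.

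**What to change.** 1. **Keep the observed-case tables.** State the denominator at each visit and label the rates as applying to subjects still in the active period.
2. **Add a by-visit status table** for ACR Pedi 30/50/70 and clinically inactive disease on a fixed denominator. Show parent-study completers who did not enrol in the extension separately, so that non-enrolment is not mixed with treatment outcome. Categories:
   - active period, responder
   - active period, non-responder
   - in withdrawal, currently responding
   - in withdrawal, not responding or relapsed
   - in re-treatment, responder
   - in re-treatment, non-responder
   - stopped for lack of efficacy
   - stopped for adverse event
   - other or missing
3. **Take status in withdrawal and re-treatment from each visit's data, not frozen at exit.** Protocol 1.2 cites a retrospective review of 26 patients in which 69% relapsed after stopping etanercept, so carrying a good response forward would mislead.
4. **Specify two details.** Use the parent-study baseline for ACR Pedi throughout, as the SAP 4.2.2 note does. Map withdrawal and re-treatment visits, which are timed from entry to those periods, to time since extension baseline.
5. **Report the long-term-benefit statement with both tables.**

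The cost is SAP wording, a visit-mapping rule and a few tables. No new data collection or imputation model is needed, but recorded reasons for stopping must distinguish lack of efficacy; the documents do not list the reason codes. The downside is possibly less favourable figures.

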- c. The month 3 to month 96 visits must occur at the study site within ± 14 days of the projected visit date based on the actual date of the baseline or active treatment early withdrawal visit. Subjects who do not experience disease relapse will continue in the withdrawal period for a total of 96 months (± 14 days) after the baseline visit of study B1801023.
- d. Subjects in the withdrawal period who experience disease relapse or discontinue from the withdrawal period for any reason (eg, for adverse events) will be seen for a re-treatment assessment visit. For subjects experiencing disease relapse, the re-treatment assessment visit should occur as soon as possible after disease relapse. Those subjects requiring re-treatment per the investigator's clinical judgment and who are otherwise eligible will be offered the option to re-start treatment with investigational product. Subjects who participate in the withdrawal period and are ineligible for the re-treatment period will be asked to participate in the observational period.
- e. Subjects who participate in the withdrawal period, and discontinue from the withdrawal period before completion of the month 96 visit, and do not participate in the re-treatment period will be asked to be followed in the observational period for a total of 96 months from the time of the baseline visit in study B1801023. Once the subject is in the observational period, he or she cannot resume investigational product for the remaining time in the study.
- f. For subjects who agree to participate in the observational period, the first observational visit will occur at the study site 30 days (± 7 days) after the re-treatment assessment visit. This visit may be waived if the subject had already been seen at the study site ≥ 30 days after the most recent dose of investigational product in either study 0881A1-3338 or B1801023.
- g. Subsequent observational visits will occur by telephone every 6 months (± 4 weeks) after the first observational visit (if conducted) or after the re-treatment assessment visit. For subjects < 18 years of age, telephone contacts will be conducted with the subject's parent or legal representative/guardian. For subjects aged ≥ 18 years, telephone contacts will be conducted with the subject or the subject's parent or legal representative/guardian. The number of telephone contacts will be adjusted based on when the subject enters the observational period.

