6.1.2.2. Withdrawal Period

Subjects who are eligible and consent to participate in the withdrawal period will have the following visits conducted:

- Subjects who enter directly into the withdrawal period will have the first post baseline visit conducted at the study site 1 month (± 7 days) after the baseline visit.
- Subjects who participated in the active treatment period of study B1801023 will have the first withdrawal visit conducted at the study site 1 month (± 7 days) after the active treatment early withdrawal visit.
- Subsequent visits will occur at the study site every 3 months after the baseline or active treatment early withdrawal visit for up to a year and then every 6 months thereafter. Subsequent visits must be scheduled within ± 14 days of the projected visit date based on the actual date of the baseline or active treatment period early

withdrawal visit. Subjects who do not experience disease relapse will continue in the withdrawal period for a total of 96 months from the time of the baseline visit in study B1801023.

The following assessments will be performed at all visits during the withdrawal period unless otherwise indicated:

1. Ensure that the subject meets inclusion/exclusion criteria that apply to the withdrawal period.
2. Those subjects who do not meet entry criteria for the withdrawal period will be asked to participate in the observational period.
3. Ensure the most recent version(s) of the informed consent/assent for withdrawal/re-treatment period has been signed and dated.
4. Collect/update contact information, including primary care physician or other treating physician.
5. Concomitant medications (DMARDs, corticosteroids, NSAIDs, and anti-infective agents) and non-drug treatments received due to an adverse event.
6. Physical examination (performed by a physician and conducted at months 12, 24, 36, 48, 60, 72, 84, and 96 only).
 - The physical examination will include completion of the Tanner Assessment for subjects <18 years or who have a score of <5 on 1 or more applicable domain(s).
7. Vital signs: Temperature, blood pressure (mmHg) and pulse rate (beats/min, after sitting for at least 5 minutes).
8. Height (cm, at months 12, 24, 36, 48, 60, 72, 84, and 96 only).
9. Weight (kg):
 - For subjects who are <18 years of age and who weigh ≤ 62 kg (at all visits).
 - For subjects who are ≥ 18 years of age or weigh > 62 kg (at months 12, 24, 36, 48, 60, 72, 84, and 96 only).

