5.3. Subject Disposition

The numbers (and percentages) of subjects who were enrolled, who took at least one dose of investigational product, who discontinued from the parent study and who completed the parent study will be summarized from FAS. The number who completed the parent study will be further broken down into the number who did and did not continue into the extension study. The numbers (and percentages) of subjects who discontinued from the extension and who completed the extension will be summarized. This will be done separately for all subjects in the extension, for all subjects who began the extension in the active treatment period, withdrawal/re-treatment period, and for subjects who began the extension in the observational period. For those subjects who began in the active treatment period, the numbers who entered withdrawal/re-treatment period, who switched to the observational period, and reason for switching, will also be tabulated. In addition, the proportion of subjects who discontinued from the extension study for any reason and for each specific reason will be tabulated. The number and percentage of subjects who completed each year of the study may be provided.

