5.4. Demography and Baseline Characteristics

Demographic, baseline characteristics (eg, subtype of JIA) and baseline disease characteristics (physician global assessment, patient/parent global assessment, Number of joints with LOM, Number of painful joints, Number of swollen joints, Pain assessment, Morning stiffness, CRP, CHAQ and HAQ. Additionally, Tender entheses score, Overall back pain VAS, Nocturnal back pain VAS, Modified Schober's test for ERA subtype; BSA of psoriasis, Physician's Global Assessment of Psoriasis for PsA subtype) data will be summarized. For continuous variables such as age, height, weight, the descriptive statistics will include the number of patients, mean, median, standard deviation, minimum, and maximum. For dichotomous variables such as sex and nominal variables such as race and ethnicity, the descriptive statistics will include the total number of patients, the count and percentage in each category. Baseline and demographic data will be summarized for subjects entered extension study (both parent study and extension study baselines), Withdrawal Analysis Set

(WAS, withdrawal period baseline), and Re-treatment Analysis Set (RTAS, retreatment period baseline).

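### Later by-visit WAS percentages for clinically inactive disease appear to be taken among subjects still in the withdrawal period, and so overstate the share of all who stopped etanercept and are inactive off drug

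*SAP*

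**What the plan says.** SAP 3.2 defines WAS as the subjects who entered the withdrawal period and adds: "Only data collected in the withdrawal period will be included". In SAP 5.9 the WAS entry reads "WAS. The reports will show all visits where data is collected". Clinically inactive disease is a yes/no endpoint, and SAP 5.9 says: "For categorical endpoints, the summary statistics will contain the frequency, percentage, and 95% confidence interval (CI) for the percentage". The base of that percentage is not named. SAP 5.16 rules out filling in absent values: "If an endpoint is missing after derivation, the missing value will not be imputed".

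The Protocol ties staying in the period to outcome. Section 6.1.2.2 says: "Subjects who do not experience disease relapse will continue in the withdrawal period for a total of 96 months", counted from the B1801023 baseline. Footnote d of the withdrawal-period Schedule of Activities sends to a re-treatment assessment visit "Subjects in the withdrawal period who experience disease relapse or discontinue from the withdrawal period for any reason". After that visit (Protocol 6.1.5 and 6.1.6) a subject takes one of two routes:

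- restarting etanercept, after which the data belong to the re-treatment analysis set (RTAS, SAP 3.3);
- entering the observational period, which collects safety and medication information but no efficacy.

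Other outputs give totals. For subjects who began in active treatment, SAP 5.3 says "the numbers who entered withdrawal/re-treatment period, who switched to the observational period, and reason for switching, will also be tabulated". SAP 5.4 plans baseline tables for WAS and RTAS, and for categorical variables "the descriptive statistics will include the total number of patients, the count and percentage in each category". SAP 5.9 also gives the number of observations at each visit for continuous endpoints.

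**The concern.** SAP 1 explains that the protocol was amended to explore how subjects fare once etanercept is withdrawn and once disease relapses. The obvious question is how many of those who stop are still well without the drug. A percentage among those still in the period does not answer it. After the exit visit a relapser is neither a success nor a failure in the WAS rows; the subject simply leaves the denominator. The rows can hold steady at a high value while most of those who stopped have relapsed.

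The target is best worded as inactive and still off drug, rather than as having stayed inactive throughout. Protocol 4.1.3 admits subjects on a good clinical response as well as on sustained inactive disease, so some entrants may not be inactive at the start.

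**Working it through.** Neither document gives an expected inactive-disease rate, a WAS size or a relapse rate for this trial, so there is no plan figure to reproduce. What follows is illustration.

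Inputs:

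- S, the share not yet relapsed at the visit: not stated. Values 0.9, 0.7 and 0.5 are used. The last is the 6-month symptom-free probability in the 26-patient retrospective series cited in Protocol 1.2.
- q, the share inactive among those remaining: assumed 0.9.
- S_prev, the value of S at the previous visit: assumed 0.75.
- D, the share of WAS whose visit has fallen due: entry assumed uniform over months 0 to 96. The 96-month end is from Protocol 6.1.2.2.
- r, the share of relapsers inactive after re-treatment: 0.5 and 1.0, assumed.

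Steps 1 to 3 take every exit to be a relapse and count relapsers as not inactive.

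**1. Relapse visit outside the row.** Row = q. Share of all who stopped (visit due) = q × S. Ratio = 1/S.

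| S | Row | Of all who stopped | Ratio |
|---|---|---|---|
| 0.9 | 90% | 0.9 × 0.9 = 81% | 1.11 |
| 0.7 | 90% | 0.9 × 0.7 = 63% | 1.43 |
| 0.5 | 90% | 0.9 × 0.5 = 45% | 2.0 |

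**2. Relapse visit windowed into the row.** New relapsers count once as not inactive, so row = q × S/S_prev and ratio = 1/S_prev. With S = 0.5 and S_prev = 0.75, the row is 0.9 × 0.5/0.75 = 60% against 45%, a ratio of 1.33. At the first row S_prev = 1 and there is no overstatement.

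**3. Can the planned totals correct the row?** Dividing the frequency by the WAS total gives q × S × D, with D = 1 − m/96 at withdrawal month m. With S = 0.7 the wanted value is 63%. At Month 24, D = 0.75 and the result is 0.9 × 0.7 × 0.75 = 47%. At Month 48, D = 0.50 and the result is 0.9 × 0.7 × 0.50 = 32%. This errs the other way, because the WAS total includes subjects whose visit was never due.

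**4. Exits for other reasons.** Take S = 0.5 and q = 0.9 (target 45%), with independent constant hazards for relapse and other exit.

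- Equal hazards: 0.5 × 0.5 = 0.25 remain, 0.375 have relapsed and 0.375 have left otherwise. Inactive and remaining: 0.9 × 0.25 = 0.225.
- Other-exit hazard one quarter of the relapse hazard: 0.5 × 0.5^0.25 = 0.420 remain. The 0.580 who left split 4:1 into 0.464 and 0.116. Inactive and remaining: 0.9 × 0.420 = 0.378.

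| Handling of other exits | Equal hazards | One quarter |
|---|---|---|
| Excluded, relapsers kept | 0.225/0.625 = 36% | 0.378/0.884 = 43% |
| Counted not inactive | 22.5% | 38% |
| Counted inactive | 0.225 + 0.375 = 60% | 0.378 + 0.116 = 49% |
| Kaplan-Meier × q | 0.5 × 0.9 = 45% | 45% |

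The first two both fall below the target, so they do not bracket it. The second and third do.

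**5. A stop-then-re-treat strategy.** Its value is S × q + (1 − S) × r. With S = 0.5 and q = 0.9 it is 0.45 + 0.25 = 70% at r = 0.5 and 0.45 + 0.50 = 95% at r = 1.0, against a row of 90%. The direction changes at r = q.

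**The case against.** The strongest reply is that the comparison target is not the SAP's. SAP 5.9 promises descriptive summaries in an open-label, single-treatment study whose primary endpoint is malignancy. It does not say that a WAS row estimates anything about all who stopped. The denominator is inferred, and visit windows are left to a programming specification that is not public (SAP 5.1). The re-treatment assessment visit is a full efficacy visit in the withdrawal-period schedule, so it may well fall in the rows. Numbers of observations are given for continuous endpoints, so attrition is partly visible. Objectives, endpoints and derivations all contain redacted text that could hold a relapse analysis.

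Much of this stands, and it limits the claim. The denominator is a natural reading, not a stated rule. Including the relapse visit changes the factor to 1/S_prev but does not bring relapsers back into later rows. A redacted relapse analysis would supply the missing estimate without changing what these rows contain. Observation numbers show how many remain, but not why the others left or whether their visit was due. Exit follows relapse and investigator judgment rather than failure of the inactive-disease criteria, so some who stay may not be inactive and some who leave for other reasons may be.

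A reader might infer that the rows are wrong by a factor of two. The documents do not support a size: S = 0.5 comes from a small retrospective series and assumes that the relapse visit lies outside the row. The 69% overall relapse in that series is given without a time, so it cannot be attached to a visit.

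**Conclusion.** The point holds as a matter of what the rows measure. If the percentages are taken among subjects in the period with data, later rows exceed the share of all who stopped and are inactive off drug, once relapsers have left and someone remains inactive. The factor is 1/S at the current visit, or 1/S at the previous visit if the relapse visit is in the row. This takes exits to be relapses and relapsers to be not inactive. The actual size is unknown.

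Two stronger readings are not supported. One is that the plan has no relapse analysis: redacted text prevents that conclusion. The other is that the rows flatter a policy of stopping and restarting on relapse: step 5 shows that the sign depends on the response to re-treatment, which RTAS reports.

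The tables are secondary and descriptive and the primary safety endpoint is untouched. The change is still worth making, because the rows address the question for which the withdrawal period was added, and the visible totals cannot be used to correct them.

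**What to change.** In SAP 5.9:

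1. Keep the WAS tables. Label them as among subjects remaining in the withdrawal period, and state whether the re-treatment assessment visit is included in the row.
2. At each scheduled visit show the numbers entered, exited for relapse or re-treatment, exited for other reasons, and not yet due.
3. Unless redacted text already does so, add a Kaplan-Meier estimate of time to relapse or start of re-treatment, censoring other exits and end of follow-up. Multiply it by the percentage inactive among those remaining, with relapse-visit records left out, to give the share inactive and off drug among all who stopped. State the assumption that other exits are unrelated to relapse and disease state.
4. As sensitivity bounds, among subjects whose visit was due, count other-reason exits once as inactive and once as not inactive. Do not exclude them while keeping relapsers.

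The cost is SAP wording and a few table rows from data already collected. It relies on the recorded reason for leaving, assumed to be on the withdrawal-period End of Phase form (Protocol 6.1.5). No readable passage defines relapse, so the SAP must name the record that identifies it. The added measure is off-drug only and does not show recovery after re-treatment, which stays with RTAS.
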